4.1.2 Exclusion Criteria

- 1. Female subjects who are pregnant or lactating or planning to become pregnant during the study period.
- 2. Hypersensitivity or intolerance to Podofilox or any component of the formulation.
- 3. History of previous unsuccessful treatment with any formulation of Podofilox.
- 4. Wart area that is greater than 10 cm².
- 5. Patients with internal anogenital and mucous membrane warts, Bowenoid papulosis, squamous cell carcinoma, active herpes lesion, or other skin abnormalities of treatment area, such as eczema, or skin that had not healed following surgery (cryosurgery, laser ablation or similar).
- 6. Primary or secondary immunodeficiency.
- 7. Patients with diabetes type I or II.
- 8. Local irritation in any treatment area that would interfere with treatment.
- 9. Use within 4 weeks prior to baseline of any: 1) treatment for anogenital warts, 2) systemic corticosteroids, or 3) systemic immunosuppressive drug.
- 10. Any medical or surgical condition in the judgment of the Investigator that may interfere with the assessment of efficacy or safety, or pose a risk to the subject.
- 11. Patients known to abuse alcohol and/or drugs, or with a history of chronic alcohol or drug abuse that may result in protocol non-compliance.
- 12. Received another investigational drug, device, or biologic within 90 days prior to the start of Screening or has planned to participate in another clinical trial while enrolled in this study.
- 13. Subjects who in the opinion of the investigator, are unlikely to be able to follow treatment instructions, protocol requirements and complete the study
- 14. Employee (or employee's family member) of the research center or private practice, CRO or Sponsor, or subjects who have a conflict of interest.

Confidential Page 27 of 59

- 15. Subjects living (e.g., siblings, spouses, relatives, roommates) in the same household cannot be enrolled in the study at the same time.
- 16. Previous enrollment in this study, current enrollment in this study at another participating site or current enrollment in another study (in parallel to this study) at another clinical research site.

4.2 Withdrawal and Early Discontinuation

A subject may voluntary withdraw from the study at any time and for any reason without prejudice to his or her future medical care. The Investigator, Sponsor, or Medical Monitor may also withdraw the subject at any time if it is medically necessary or in the interest of subject safety. Additional reasons for premature discontinuation of study drug may include adverse events and major non-compliance with study procedures as described below. The withdrawal of a patient from study drug by the Investigator should be discussed with the Medical Monitor before the patient stops study drug, whenever possible.

A subject will be discontinued from this study if any of the following criteria are met:

- Withdrawal of consent by the subject is received.
- In the opinion of the Investigator, it is not in the subject's best interests to continue in the study.
- Occurrence of an Adverse Event (AE) or Serious Adverse Event (SAE), which, in the opinion of the Investigator, warrants discontinuation of the subject from the study.
- Pregnancy (refer to Section 7.6).
- Significant non-compliance with study procedures that would interfere with the study results or increase the subject's risks in the study.
- If subject is deemed to be a treatment failure, which is defined as worsening of condition (increase in the number of warts, in the size of the warts, or other clinical signs as determined by the Investigator) and requiring alternate or supplemental therapy for the treatment of external anogenital warts during the study.
- The subject's medication code is unblinded.
- Subject did not meet, or no longer meets, the entry criteria.
- The subject is lost to follow-up. The investigator will document efforts to attempt to reach the subject twice by telephone and will send a certified follow-up letter before considering that subject lost to follow-up. All attempts must be thoroughly recorded.
- Investigator discretion.

Subjects discontinuing due to "treatment failure" will be included in the PP population analysis as treatment failures, and will have alternative treatment recommended by the Investigator. Subjects discontinued prematurely from the study for any other reason (i.e., noncompliance, or withdrawal of consent, etc.) will be excluded from the PP population, but included in the ITT population, using Last Observation Carried Forward (LOCF).

In the case if subject discontinues prematurely, the Investigator will perform Early Termination (ET) visit, capturing the reason for discontinuation and performing assessments of EOS visit (Section 6.3.4).

If a subject does not return for a scheduled visit, every effort will be made to contact the subject and document the End of Study (EOS) visit assessments. The patient should at least be contacted twice by phone and, if no answer, by registered letter within a week. The Investigator must document the primary reason

Confidential Page 28 of 59

for discontinuation of a study subject in the source document and on the appropriate electronic case report form (eCRF).

Randomized subjects who discontinue due to an adverse event will have all events documented and followed to satisfactory resolution, as detailed in Section 7.4.

After a subject has been discontinued, he/she will not be allowed to re-enroll in the study at any facility.

4.3 Contraception and Pregnancy Avoidance Measures

The study will require that all female subjects of childbearing potential practice a method of birth control with a reliability of at least 90% defined as follows:

- Female subjects must be surgically sterile, postmenopausal (for at least one year).
- Female subjects not surgically sterile or postmenopausal (for at least one year), and non-vasectomized male subjects, must practice at least one of the following methods of birth control:
 - Total abstinence from sexual intercourse (minimum one complete menstrual cycle prior to Screening visit, throughout the study).
 - A vasectomized partner.
 - O Hormonal contraceptives (oral, parenteral, or transdermal) for at least three months prior to study drug administration or intrauterine contraception/device double-barrier method (such as male condom, female condom, diaphragm, sponge, or cervical cap *together with* spermicidal foam/gel/film/suppository).

Sexually active study participants must agree to abstain from sexual activity of any kind throughout the treatment period to prevent cross- and reinfection by HPV.

If a subject becomes pregnant during the participation in the study, the Investigator will immediately discontinue the patient from the study and contact the Medical Monitor, Biorasi Safety Team, or Sponsor. Diligent efforts will be made to determine the outcome for all pregnancy exposures in the clinical trial. Information on the status of the mother and the child will be forwarded to the Biorasi Safety Team using the Pregnancy Data Collection Form. Generally, follow-up will occur within 6 to 8 weeks following the estimated delivery date. Any premature termination of the pregnancy will be reported.

Confidential Page 29 of 59

5 STUDY DRUG ADMINISTRATION

5.1 Identity of Study Drug(s)

The term *study drug* is used to refer to the Test, Reference and Placebo drug products.

5.1.1 Formulation of Study Drug

Study drug in this study will be supplied as matching 3.5 g of clear gel in aluminum tubes with an applicator tip, labeled for a blinded study.

- **Test Drug:** Podofilox Topical Gel 0.5%, manufactured for Hyloris Developments SA by Perrigo Company Ltd.
- **RLD:** Condylox® Gel 0.5%, manufactured for Allergan Pharmaceuticals, by DPT Laboratories, Ltd., distributed by Actavis Pharma, Inc.
- **Placebo:** Vehicle of the test drug, manufactured for Hyloris Developments SA by Perrigo Company Ltd.

5.2 Packaging and Labeling

The study drug tubes to be dispensed to the subject will be packaged and labeled in accordance with Good Manufacturing Practice. Each individual tube of the study drug will be diaper-labelled and look identical.

5.3 Storage of the Study Drug

Storage temperature for study drug is 20-25°C (68-77°F). All study medication supplies must be kept in a secure cabinet or room. Only the designated study personnel will have access to study medication supplies.

The Investigator will maintain temperature continued monitoring of the study drug with temperature readings. All temperature excursions must be reported to Biorasi using Temperature Excursion Form. The study drug that experienced excursions must be quarantined until the Medical Monitor / Sponsor's approval on future use.

5.4 Reserve Sample Retention

When a site receives a shipment of the study drug, study pharmacist, or designated study personnel will separate one randomly selected set of study drug for retention. The retention samples will be marked accordingly, stored securely along with sealed randomization codes for FDA use (according to Guidance for Industry - Handling and Retention of BA and BE Testing Samples.; 2004, and CRF 320.38 and 320.63). For all subsequent shipments, the same procedure is to be followed.¹⁷ Retention samples will be stored under the same temperature conditions as the study drug for use in the study by subjects.

The Investigator will store the retention samples of the study drug until such time or until notification is received from the Sponsor that the samples are no longer required and proper instruction of what to do with the sample is given by the Sponsor.

Confidential Page 30 of 59

5.5 Treatment Assignment (Randomization)

Randomization will be performed using an Interactive Response Technology (IRT) system that is fully integrated with the Electronic Data Collection (EDC) system. Randomization and treatment assignment will be determined at the time the subject has met all eligibility criteria and is ready for enrollment. Subjects will be randomized in a 3:3:1 ratio to receive the test product, RLD, or placebo.

Subjects will be stratified by gender. A balanced distribution amongst male and female subjects across the study in all three study groups will be maintained by the IRT system which will assign subjects to the treatment arm and specify the kit number to be dispensed.

The randomization scheme will be held by the independent third party throughout the conduct of the study (through database lock) and will not be available to the Hyloris Developments SA, Biorasi, Investigator, or study staff, or to clinical staff who could have an impact on the outcome of the study.

5.6 Blinding

This is a double-blind study, thus Sponsor, Biorasi, Investigator, site staff, study monitors, and subjects will be blinded to the randomization scheme. The packaging of the test, RLD products and placebo will be similar in appearance to make no difference in treatment to the subjects and study staff.

The blinding code must not be broken except in emergency situations for which the identification of the study treatment of a subject is required by the Investigator to complete a serious adverse event report. In such situations, the Medical Monitor or the Investigator will use the IRT system to unblind the treatment for the individual subject. Unblinded information will be held by designated individual(s), and the date and reason for breaking the blind must be recorded.

As the study is blinded, the Investigator should promptly document and report to the Sponsor any premature unblinding (e.g., accidental unblinding, unblinding due to a serious adverse event) of the investigational product(s).

5.7 Treatment Administration

5.7.1 Study Drug Dispensation and Application

Subjects will receive the randomized treatment along at the Baseline Visit (Day 0) with a Subject Diary Card, written instructions and precautions. Prior to dispensation Investigator will measure the weight of the study medication using electronic scales. Each subject will be instructed by the Investigator on proper application technique. The Investigator will identify which warts should be treated during the application training session at the Baseline visit.

Following application instructions will be provided to the subject:

1. This medication is for topical use only. Apply it on the warts pointed out by your doctor. It should be applied once in the morning and again in the evening (at bedtime) for 3 days followed by a 4-day rest period. If the warts do not go away, your study doctor will decide if another cycle of

Confidential Page 31 of 59

- treatment is necessary. This cycle may be repeated up to 4 times. If the warts do not go away after 4 weeks of treatment, your study doctor will advise you on the alternative treatment methods.
- 2. To apply the study drug, use an applicator tip or your finger. Apply a small amount of medication to the wart to cover it. Application on the surrounding normal tissue should be minimized. If the genital wart is in a skin fold, spread the skin apart and apply the medicine. Allow the treated skin to dry before releasing the skin fold. Wash your hands thoroughly with soap and water before and after each application.
- 3. This medication should be used only as directed by study doctor. You should wash your hands thoroughly before and after each application. It is for external use only. Avoid contact with the eyes. If contact occurs, immediately wash with plenty of water and contact your study doctor.
- 4. Do NOT use large amounts. Maximum amount that can be applied is 0.5 gram per day (or 0.25 gram per one application). Do NOT apply more often or use for a longer period than directed. Your condition will not clear faster, and the chance for side effects may be increased.
- 5. Do NOT use this medication for any disorder other than for External Anogenital Warts. The medication should NOT be used in the vagina or in the rectum or on any open wounds. You should not wash the medication off the wart area unless you experience excessive pain, burning, or itching.
- 6. Report any signs of adverse reactions to your study doctor. If the area you are putting study medication on is bleeding or swollen, or if there is excessive pain, burning or itching, stop applying it and contact your doctor.
- 7. Do not have sexual contact of any kind during the treatment period.
- 8. The study drug is flammable and must be kept away from open flames.

The subject will return used tubes of the study drug at the next visit along with completed Subject Diary Card. The Investigator will measure the weight of returned study medication using electronic scales. Measured weight of the study medication will be documented in a Study Drug Accountability Log.

If an additional treatment cycle is required, the Investigator will dispense the returned tube. If the remaining amount of the study drug in the used tube is not sufficient for another treatment cycle, study site will dispense a new tube of the study drug using the IRT system. The Investigator will measure the weight of study medication using electronic scales prior to providing to subject.

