Podofilox (podophyllotoxin) is a patient-applied antimitotic drug that causes wart necrosis. Podofilox solution (using a cotton swab) or Podofilox gel (using an applicator tip or a finger) should be applied to anogenital warts twice a day for 3 days, followed by 4 days of no therapy. This cycle can be repeated, as necessary, for up to four cycles. The total wart area treated should not exceed 10 cm², and the total volume of Podofilox should be limited to 0.5 mg of the gel per day. Health-care provider should describe proper application technique and identify which warts should be treated. Mild to moderate pain or local irritation might develop after treatment. Podofilox is contraindicated in pregnancy.²

Imiquimod is a patient-applied, topically active immune enhancer that stimulates production of interferon and other cytokines. Imiquimod 5% cream should be applied once at bedtime, three times a week for up to 16 weeks.³ Similarly, Imiquimod 3.75% cream should be applied once at bedtime, but is applied every night.⁴ With either formulation, the treatment area should be washed with soap and water 6–10 hours after the application. Local inflammatory reactions, including redness, irritation, induration, ulceration/erosions, and vesicles might occur with the use of Imiquimod, and hypopigmentation has also been described.⁵ A small number of case reports demonstrate an association between treatment with Imiquimod cream and worsened inflammatory or autoimmune skin diseases (e.g., psoriasis, vitiligo, and lichenoid dermatoses).⁶ Data from studies of human subjects are limited regarding use of Imiquimod in pregnancy, but animal data suggest that this therapy poses low risk.²

Sinecatechins is a patient-applied, green-tea extract with an active product (catechins). Sinecatechins 15% ointment should be applied three times daily (0.5 cm strand of ointment to each wart) using a finger to ensure coverage with a thin layer of ointment until complete clearance of warts is achieved. This product should not be continued for longer than 16 weeks. 9-11 The medication should not be washed off after use. Genital, anal, and oral sexual contact should be avoided while the ointment is on the skin. The most common side effects of Sinecatechins are erythema, pruritus/burning, pain, ulceration, edema, induration, and

Confidential Page 20 of 59

[†] Might weaken condoms and vaginal diaphragms

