1.2 Background to the Study Drug

Podofilox is an antimitotic drug which can be chemically synthesized or purified from the plant families *Coniferae* and *Berberidaceae* (e.g. species of *Juniperus* and *Podophyllum*).

RLD Condylox® Gel 0.5% is formulated for topical administration and supplied in 3.5 g aluminum tubes with an applicator tip. Each gram of drug substance contains 5 mg of Podofilox in a buffered alcoholic gel containing alcohol, glycerin, lactic acid, hydroxypropyl cellulose, sodium lactate, and butylated hydroxytoluene.

Podofilox Gel 0.5% must be applied to the warts surface with the applicator tip or finger. The Podofilox Gel 0.5% may cause skin irritation, and hence must not be applied to the unaffected skin areas. Treatment cycle consists of twice daily applications (morning and evening) for three consecutive days followed by a four day "rest" period. This one-week cycle may be repeated until there is no visible wart tissue or for a maximum of four cycles in total. Treatment should be limited to 10 cm² or less of wart tissue and to no more than 0.5 g of the gel per day.

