6.3.2 Visit 2: Baseline Visit (Day 0)

- Adverse Events Assessment
- Concomitant and Prohibited Therapies Review
- Assessment of Vital Signs
- Physical Examination
- Urine Pregnancy Test
- Visual Inspection of EAWs
- Assessment of Local Application Site Reactions
- Eligibility Criteria Check
- Randomization
- Study Drug Dispensation
- Subject Diary Card Dispensation
- Training on Study Drug Application
- Training on Subject Diary Card completion and contraception methods
- Schedule next visit to occur within window

6.3.3 Visits 3-6 (Day 7 [Week 1], Day 14 [Week 2], Day 21 [Week 3], and Day 28 [Week 4])

The following procedures will be performed:

- Subject Diary Card Return, Review and Dispensation
- Adverse Events Assessment
- Concomitant and Prohibited Therapies Review
- Assessment of Vital Signs

Confidential Page 38 of 59

- Assessment of Local Application Site Reactions
- Visual Inspection of EAWs. In the case there is a total disappearance of all warts within all treated areas at visits 2, 3, 4, or 5, this visit will be considered an End of Study (EOS) visit. In the case where reduction of warts is absent or incomplete, a new treatment cycle will be initiated for a maximum of four cycles in total for the subject.
- Study Drug Return and Accountability
- Study Drug Dispensation

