8.1 Subject Population/Data Sets to Be Evaluated

The subject populations are defined as follows:

- 1. Safety Population: The safety population includes all randomized subjects who received and used study product.
- 2. **Modified Intent-to-Treat (mITT) Population:** A modified intent-to-treat population includes all subjects who are randomized, applied at least one dose of assigned product, and returned for at least one post-baseline evaluation visit.
- 3. **Per Protocol (PP) Population:** all randomized subjects who met all inclusion/exclusion criteria, had no protocol violations that would affect the treatment evaluation, were compliant with applying study product, and returned to the study site for the primary endpoint evaluation at four days (± 5 days) after the last day of the last cycle of treatment. Compliant subjects are defined as those who used at least 75% and no more than 125% of study drug doses until treatment success or four cycles of treatment.

Subjects discontinuing due to "treatment failure" will be included in the PP population analysis as treatment failures, and will have alternative treatment recommended by the Investigator. Subjects discontinued prematurely from the study for any other reason (i.e., noncompliance, or withdrawal of consent, etc.) will be excluded from the PP population, but included in the mITT population, using Last Observation Carried Forward (LOCF).

The results in the PP population will be considered definitive for therapeutic equivalence with those in the mITT population considered supportive. The results in the mITT population will be considered definitive

Confidential Page 46 of 59

for superiority of each active treatment to placebo with those in the PP population considered supportive. Safety analyses will be performed using the Safety population.

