12.2 Appendix B. Schedule of Events

	Screening Visit 1	Baseline Visit 2	Treatment Period			
Study Visit			Visit 3	Visit 4	Visit 5	EOS/ET Visit 6
Visit Day	Day -14 to -1	Day 0	Day 7 (±1 day)	Day 14 (±1 day)	Day 21 (±1 day)	Day 28 (±5 day)
Informed Consent	X					
Subject Demographics	X					
Medical History	X					
Concomitant and Prohibited Therapies Review	X	X	X	X	X	X
Vital Signs	X	X	X	X	X	X
Physical Examination	X	X				X
Visual Inspection of EAWs ¹	X	X	X	X	X	X
Serology test for HIV ²	X					
Test for Hepatitis B, C	X					
Test for Syphilis ³	X					
Urine Pregnancy Test	X	X				X
Eligibility Criteria Check	X	X				
Randomization		X				
Training on Study Drug Application		X				
Training on Subject Diary Card completion and contraception methods		X				
Study Drug Dispensation		X	X	X	X	
Assessment of Local Application Site Reactions		X	X	X	X	X
Adverse Events Assessment	X	X	X	X	X	X
Study Drug Return and Accountability			X	X	X	X
Subject Diary Card Return and Review			X	X	X	X
Subject Diary Card Dispensation		X	X	X	X	
Histological confirmation of diagnosis ⁴	X			_		

¹ If total disappearance of all warts is achieved within all treated areas at visits 2, 3, 4, or 5, respective visit will be considered an End of Study (EOS) visit. In the case where reduction of warts is absent or incomplete, a new treatment cycle will be initiated for a maximum of four cycles in total for the subject.

² Test may not be repeated if the subject has negative HIV test results within 4 weeks before Baseline. Copy of the test result needs to be filed with the study records.

³ If required by applicable local regulations.

⁴ Histological confirmation will be obtained if there is any doubt of the diagnosis. *Confidential*

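### Subject instruction 1 in protocol 5.7.1 and the Day 28 dispensing entries in 6.3.3 conflict with the four-cycle maximum stated elsewhere

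*Protocol*

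**What the plan says.** **Number of cycles.** The protocol synopsis, protocol 3.1 and SAP 5.1 set a maximum of four weekly cycles and list the application days, the last being Day 24. Protocol 6.3.3 and footnote 1 of Appendix B say that, for a subject not yet cleared, "a new treatment cycle will be initiated for a maximum of four cycles in total for the subject". Instruction 1 in protocol 5.7.1 says instead: "This cycle may be repeated up to 4 times". Its next sentence reads: "If the warts do not go away after 4 weeks of treatment, your study doctor will advise you on the alternative treatment methods".

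**Dispensing at Day 28.** The heading of protocol 6.3.3 covers "Visits 3-6 (Day 7 [Week 1], Day 14 [Week 2], Day 21 [Week 3], and Day 28 [Week 4" and so takes in Visit 6. The single list below it includes "Study Drug Dispensation" and dispensing of a diary card, with no exception for Day 28. Appendix B and the schedule in SAP 3.2 mark both items at Visits 2 to 5 only. Protocol 6.3.4, the end-of-study and early-termination list, has return of drug and diary but dispensing of neither.

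**Daily amount (minor).** The background in protocol 1.1 says "the total volume of Podofilox should be limited to 0.5 mg of the gel per day". Protocol 1.2 limits treatment "to no more than 0.5 g of the gel per day", and the synopsis, 3.1 and 5.7.1 also use grams.

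**The concern.** The two conflicting passages are operative text. Instruction 1 is read by subjects who apply an antimitotic gel to themselves at home, and the 6.3.3 list is what site staff would work from at a visit. A subject could take instruction 1 to allow four further cycles after the first. A site that followed the 6.3.3 list item by item would hand out drug and a new diary at Day 28.

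The paragraph in 5.7.1 on further cycles makes re-dispensing depend on another cycle being required, but it does not repeat the maximum. Drug handed out at Visit 6 would be used after the last scheduled visit, so no scheduled wart inspection, reaction score, diary review or drug return would follow. Unscheduled visits (6.3.5) and adverse event follow-up (6.2.1.8 and 7.4) would remain. What is at stake is avoidable extra exposure and inconsistent practice between sites.

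**Working it through.** **1. Reproduce the planned course.** With three application days per weekly cycle, the days are 7c + d for c = 0, 1, 2, 3 and d = 1, 2, 3. This gives Days 1–3, 8–10, 15–17 and 22–24, exactly the 12 days listed in the synopsis, 3.1 and SAP 5.1. At two applications a day, 12 × 2 = 24 applications.

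**2. Literal reading of instruction 1.** One cycle plus four repeats is 1 + 4 = 5 cycles, so 5 × 3 = 15 days and 15 × 2 = 30 applications. The fifth cycle would fall on 7 × 4 + (1, 2, 3) = Days 29, 30 and 31, after the nominal Day 28 visit and outside the listed days.

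**3. Difference in maximum gel**, taking the 0.5 g per day in 3.1 and 5.7.1:

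- four cycles: 12 × 0.5 = 6.0 g
- five cycles: 15 × 0.5 = 7.5 g
- difference: 1.5 g, and 1.5 / 6.0 = 25%

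**4. Visit 6 entries side by side.**

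| Place | Drug dispensed at Visit 6 | Diary dispensed at Visit 6 |
|---|---|---|
| Protocol 6.3.3 list (Visits 3–6) | listed | listed |
| Protocol 6.3.4 (EOS/ET) | not listed | not listed |
| Protocol Appendix B | not marked | not marked |
| SAP 3.2 | not marked | not marked |

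The 6.3.3 list also conflicts with itself: it contains dispensing for a range of visits that includes Day 28, and it states the four-cycle maximum, which has been used up by Day 28.

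**5. Unit in section 1.1.** 0.5 g is 500 mg, and 500 / 0.5 = 1,000, so the two statements of the daily amount differ by a factor of 1,000.

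**The case against.** The strongest reply is that the plan, read as a whole, leaves little doubt.

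- The 6.3.3 list carries the four-cycle maximum.
- 6.3.4 classes a subject not cleared at Day 28 as a treatment failure and sends that subject to end-of-study procedures.
- In instruction 1, the sentence before the disputed one leaves each further cycle to the study doctor, and the sentence after it turns to alternative treatment after four weeks. Instruction 4 warns against longer use than directed.
- Tubes come back at each visit and are handed out again by the Investigator.
- Section 1.1 is background; subjects and sites work from passages that use grams.

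All of this stands. It limits the point to wording but does not remove it, because a subject instruction and a visit checklist should not need the rest of the protocol to be read correctly.

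A reader might go further and infer that the per-protocol rule would let a fifth cycle through, since 30 / 24 = 125% sits on the upper limit of "at least 75% and no more than 125% of study drug doses until treatment success or four cycles of treatment". The documents do not support a consequence for the analysis:

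- Drug dispensed at Visit 6 would be used after the endpoint had been assessed and after the last scheduled diary return (6.2.3), so it would neither change the outcome nor enter the compliance percentage.
- A subject who still held a tube and restarted before a late Visit 6 (the window runs to Day 33) would be acting without the doctor's decision that instruction 1 requires.
- In either case the per-protocol definition separately requires freedom from violations affecting the evaluation, and SAP 7.5.3 excludes major deviations after a classification meeting before database lock.

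Nor can every subject not cleared at Day 28 be counted as likely to receive more drug, because 6.3.4 and the schedule list no dispensing at that visit.

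**Conclusion.** The point holds as a conflict between operative passages. Instruction 1 of 5.7.1, on a literal reading, and the Visit 6 entries of 6.3.3 leave further dosing open. The synopsis, 3.1, 6.3.4, Appendix B, SAP 3.2 and SAP 5.1 point to four cycles with nothing dispensed at Day 28, as does the rest of 6.3.3.

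The size is one cycle: 6 applications, or at most 1.5 g of gel, which is 25% above the four-cycle course. That rests on two applications a day for three days per cycle and on the 0.5 g daily figure. It is the gap between two readings, not a forecast of what subjects would receive.

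The documents do not show that a fifth cycle was planned. No effect on the per-protocol population, the bioequivalence result or power is shown; the sample-size inputs in SAP 5.3 do not involve the number of cycles. The unit in section 1.1 is a minor slip in background text. No view is taken here on which clinical rule or amount is right.

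**What to change.** - Reconcile instruction 1 of protocol 5.7.1 with the four-cycle statements in the synopsis, 3.1, 6.3.3 and Appendix B, so that the number of cycles reads the same everywhere, including on the instruction sheet given to subjects.
- Reconcile the drug and diary dispensing entries of 6.3.3, as they apply to Visit 6, with 6.3.4, Appendix B and SAP 3.2.
- As a tidy-up, reconcile the unit of the daily gel amount in 1.1 with 1.2, 3.1 and 5.7.1.

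The sponsor's clinical team settles the content. The cost is a few words in the protocol and a corrected instruction sheet, with no added subjects, visits or analyses. No change to the per-protocol definition is needed on this account.
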